12.0 CRITERIA FOR REMOVAL FROM STUDY

Patients will begin dosing on Cycle 1 Day 1 (C1D1) according to assigned dose level and arm with cycle length of 28 days. Individual patients will continue on mirdametinib or mirdametinib with fulvestrant until progression of disease, unacceptable toxicity, or other reason for treatment discontinuation. Patients with documented progression of disease may be allowed to continue on study if the patient is tolerating treatment, and in the opinion of the investigator, the patient is deriving clinical benefit from continuing study treatment and continuation of treatment is approved by the investigator. If said patient continues treatment post progression, they will require reconsent.

Patients may be removed from study for the following reasons, including but not limited to:

- Progression of Disease (with exception as above)
- Unacceptable toxicity, with attention to DLT as described in [Section 15.3](#)
- Noncompliance with protocol
- Concurrent illness compromising ability to fulfill protocol requirements
- Requirement for alternative treatment in the opinion of the investigator
- Pregnancy
- Loss to Follow up
- Withdrawal of Consent
- Death
- Study Termination

The clinical trial may be discontinued or terminated in case of an unacceptable risk, any relevant toxicity, or a negative change in the risk/benefit assessment. This might include the occurrence of AEs which character, severity or frequency is new in comparison to the existing risk profile. In addition, any data deriving from other clinical trials or toxicological studies which negatively influence the risk/benefit assessment might cause discontinuation or termination of the study.

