At each step of the 3+3 design, the investigators will review all available safety and PK data in the current Dose Level and decide about the appropriate next step. The subjects will become evaluable for the 3+3 decisions if they complete Cycle 1 and receive at least 80% of assigned drug doses, or if they exhibit a DLT in Cycle 1.

The starting dose of mirdametinib as single agent in each Dose Level escalation will be as follows:

- Dose Level 1: **mirdametinib 4 mg BID PO**, given continuously
- Dose Level 2: **mirdametinib 6 mg BID PO**, given continuously
- Dose Level 3: **mirdametinib 8 mg BID PO**, given continuously
- The de-escalation (Dose Level -1) may evaluate **mirdametinib 3 mg BID** given continuously, and (Dose Level -1INT) may evaluate **mirdametinib 3 mg BID** given on a 3 weeks on, 1 week off schedule. These de-escalation Dose Levels will be evaluated at investigator's discretion after the higher dose of mirdametinib is not tolerated. The de-escalation Dose Levels will be started only if the benefit-risk ratio is acceptable at the investigator's opinion.

The 3+3 decisions in Part 1 of Arm 2 will be made as follows.

1. Dose Level 1 (**mirdametinib 4 mg BID PO** given continuously)
 - a. Up to 3 subjects will be treated with mirdametinib as single agent at the dose of **4 mg BID PO** given continuously.

Memorial Sloan Kettering Cancer Center
[name]
[name]

- b. If 1 of the first 3 evaluable subjects in Dose Level 1 exhibit a DLT in Cycle 1, then Dose Level 1 will be expanded (see #2 below)
- c. If 0 of the first 3 evaluable subjects in Dose Level 1 exhibit a DLT in Cycle 1, then the dose of mirdametinib as single agent will be escalated to Dose Level 2 (**6 mg BID** given continuously) (see #4 below)

2. Dose Level 1 expansion:

- a. A sufficient number of subjects will be treated with mirdametinib as single agent at the dose of **4 mg BID PO** given continuously to accrue 6 evaluable subjects.
- b. If ≤ 1 of 6 evaluable subjects in the starting Dose Level exhibit a DLT in Cycle 1, then the dose of mirdametinib as single agent will be escalated to Dose Level 2 (**6 mg BID** given continuously) (see #5 below).
- c. If ≥ 2 of the first 3 evaluable subjects or ≥ 2 of the 6 evaluable subjects in Dose Level 1 exhibit a DLT in Cycle 1, then the mirdametinib dose will be de-escalated (see #3 below).

3. Dose Level -1 (de-escalation Dose Level **3 mg BID PO** given continuously)

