- d. If ≥ 2 of the first 3 evaluable subjects or ≥ 2 of the 6 evaluable subjects in Dose Level 2 exhibit a DLT in Cycle 1, then **mirdametinib 4 mg BID PO** given continuously will be declared as the recommended dose for Part 2 (RP2D).

6. Dose Level 3 (Dose Level escalation **8 mg BID PO** given continuously)

- a. Up to 3 subjects will be treated with mirdametinib as a single agent at the dose of **8 mg BID PO** in Dose Level 3
- b. If ≤ 1 of the first 3 evaluable subjects in Dose Level 3 exhibit a DLT in Cycle 1, then a sufficient number of subjects will be treated with mirdametinib **8 mg BID PO** given continuously to accrue 6 evaluable subjects.
- c. If ≤ 1 of 6 evaluable subjects in Dose Level 3 exhibit a DLT in Cycle 1, then **mirdametinib 8 mg BID PO** given continuously will be declared as the recommended dose for Part 2 (RP2D).
- d. If ≥ 2 of the first 3 evaluable subjects or ≥ 2 of the 6 evaluable subjects in Dose Level 3 exhibit a DLT in Cycle 1, then **mirdametinib 6 mg BID PO** given continuously will be declared as the recommended dose for Part 2 (RP2D).
- e. The dose of mirdametinib as single agent will not be escalated above **8 mg BID PO** given continuously.

Arm 2 – Part 2 (expansion cohorts for mirdametinib as single agent)

One or more expansion cohorts (up to 30 subjects each) will be started, either in parallel or sequentially depending on the results of Part 1. The purpose will be to evaluate the efficacy and safety of the RP2D of mirdametinib as single agent (as determined in Part 1 of Arm 2) in the subjects with advanced solid cancers (with the exception of colorectal, small bowel, biliary and ampullary cancers) harboring activating mutations in MEK1/2.

Memorial Sloan Kettering Cancer Center
[name]
[name]

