For the initial parts of both arms, these utilize 3+3 design with arm 1 utilizing dose de-escalation as necessary, and arm 2 utilizing this design to escalate to MTD or RP2D. In the dose expansion cohorts of arm 1, the mirdametinib RP2D will be administered in combination with the standard recommended dose of fulvestrant with the primarily efficacy endpoint, and in dose expansion cohorts of arm 2, the mirdametinib will be given as monotherapy at the RP2D. Per MSKCC clinical research guidelines in CR426, "Expansion Cohorts in Phase I Clinical Trials", for expansion cohorts of size less than 30, a sample size justification is not required. Further, requirements for stopping rules for lack of efficacy (futility) are also not required for cohorts of less than 30 patients. Assuming a 10% low unpromising response rate (null hypothesis), and a response rate $\geq 25\%$ as a promising rate of response (alternative hypothesis), and $n = 28$ in each expansion cohort, this will provide 86% power to reject the null hypothesis if at the end of the trial at least 5 / 28 responses are observed in each cohort. Type I error is 14% for each

expansion cohort. The 10% null response rate is justified as an approximation of the standard historical rate in breast tumors treated with fulvestrant. For example, the null response rate in Solar-1 trial was 12.8%³³ and the null response rate in the Paloma-3 trial was 6.3%.³⁴

The two arms of the study will be statistically analyzed separately. Given the type I error above of 14% for any one expansion cohort, each arm (with at most two cohorts) yields a family wise error rate of $1-(1-0.14)^2 = 26\%$. If one chooses to consider the (at most) four expansion cohorts simultaneously, this yields an overall family wise error rate of $1-(1-0.14)^4 = 45\%$. While we acknowledge that this is high when all expansion cohorts are considered, first these cohorts are exploratory and second the two arms are clearly biologically different and are being treated with differing drug regimens, therefore they will be analyzed separately, thus the appropriate family wise error rate to consider for this study is that of 2 expansion cohorts, or 26%.

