In the safety run in of arm 1, a minimum of six and as many as 12 DLT-evaluable patients are required. In the dose expansion cohorts of arm 1, the mirdametinib RP2D will be administered in combination with the standard recommended dose of fulvestrant with the primarily efficacy endpoint, and in dose expansion cohorts of arm 2, the mirdametinib will be given as monotherapy at the RP2D. For these expansion cohorts, as explained above, each will be deemed promising if at the end of the study at least 5 / 28 responses (CR or PR) are observed. This part of the study will enroll $2 * 28 = 56$ efficacy evaluable patients (28 patients on each of two expansion cohorts). Exploratory future cohorts, such as subjects with hormone receptor-positive, HER2-negative metastatic breast cancer exhibiting OncoKB defined activating mutations in BRAF, CRAF, or MEK1/2 (section 4.2) are not included in this analysis. To account for non-evaluable patients, we will have a goal total enrollment of 60 patients. This part of the study is planned to accrue approximately 2 patients per month and it is expected to complete accrual in 3 years.

In the dose escalation part of arm 2 (mirdametinib monotherapy in MEK1/2 mutant patients), we anticipate as few as 6 DLT-evaluable patients and as many as 18 DLT-evaluable evaluable patients will be required, the precise number of patients enrolled in this arm is pending the observed toxicity of mirdametinib monotherapy in dose escalation. This part of the study will take approximately nine months to complete accrual, assuming two patients per month are accrued. The specific expansion cohorts for this arm of the trial are pending the observed responses by genotype and cancer lineage in this arm of the protocol. However, as with arm 1, as explained above, each expansion cohort will be deemed promising if at the end of the study at least 5 / 28 responses (CR or PR) are observed. As we also anticipate as many as two expansion cohorts of patients on this arm of the study, this arm will also require as many as $2 * 28 = 56$ efficacy evaluable patients with a goal total enrollment of 60 patients which will take 3 years to accrue.

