15.3 Dose Limiting Toxicities

The severity of adverse events (AEs) reviewed as potential dose-limiting toxicity (DLT) will be graded according to the CTCAE V.5.0. classification.

The occurrence of any of the following AEs during Cycle 1 (Day 1 – Day 28) will be considered a DLT, except for those AEs clearly related to disease progression or intercurrent illness.

Hematologic:

1. Grade 4 or greater hematologic toxicity (neutropenia, thrombocytopenia, or anemia)
2. Grade 3 febrile neutropenia (absolute neutrophil count [ANC] < 1000/mm³ with a single temperature of > 38.3°C (101°F) or a sustained temperature of ≥ 38°C (100.4°F) for > 1 hour)
3. Grade 3 thrombocytopenia with clinically significant bleeding

Non-hematologic:

1. Grade 2 or greater ocular toxicities leading to reduced visual acuity limiting ADL, glaucoma, retinal detachment, or retinal vascular disorder
2. NYHA class III or IV left ventricular dysfunction
3. Grade 3 or greater non-hematologic toxicity that is clinically significant with the following exceptions:
 - a. Toxicity (other than rash) that starts to resolve within 3 days of initiating optimal supportive care
 - b. Grade 3 rash that resolves to grade 1 or less within 7 days of initiating optimal supportive care
 - c. Grade 3 laboratory abnormalities that are not associated with clinical sequelae (e.g., isolated lactate dehydrogenase elevation) and resolves to Grade ≤1 within 3 days of initiating optimal supportive care
 - d. Grade 3 or 4 electrolyte laboratory abnormalities that last up to 72 hours, are not clinically complicated, and resolve spontaneously or respond to conventional medical interventions
 - e. Grade 3 or 4 amylase or lipase elevation that is not associated with symptoms or clinical manifestations of pancreatitis
 - f. Alopecia
4. Grade 4 non-hematologic toxicity, with the exception of those listed above, regardless of clinical significance or duration
5. Hy's law criteria (Grade ≥ 2 bilirubin in conjunction with grade ≥2 transaminase and without elevation of alkaline phosphatase)

In addition, clinically important or persistent toxicities not included above may also be considered a DLT at the discretion of the investigator after consultation with the SpringWorks physician.

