16.4 Data and Safety Monitoring

The Data and Safety Monitoring Plan utilized for this study will be aligned with the [MSK DSM Plan](#), where applicable.

The Data and Safety Monitoring (DSM) Plans at Memorial Sloan Kettering were approved by the National Cancer Institute in August 2018. The plans address the new policies set forth by the NCI in the document entitled "[Policy of the National Cancer Institute for Data and Safety Monitoring of Clinical Trials](#)".

There are several different mechanisms by which clinical studies are monitored for data, safety and quality. At a departmental/PI level there exists procedures for quality control by the research team(s). Institutional processes in place for quality assurance include protocol monitoring, compliance and data verification audits, staff education on clinical research QA and two institutional committees that are responsible for monitoring the activities of our clinical trials programs. The committees: *Data and Safety Monitoring Committee (DSMC)* for Phase I and II clinical trials, and the *Data and Safety Monitoring Board (DSMB)* for Phase III clinical trials, report to the Deputy Physician-in-Chief, Clinical Research.

The degree of monitoring required will be determined based on level of risk and documented.

The MSK DSMB monitors phase III trials and the DSMC monitors non-phase III trials. The DSMB/C have oversight over the following trials:

- MSK Investigator Initiated Trials (IITs; MSK as sponsor)
- External studies where MSK is the data coordinating center
- Low risk studies identified as requiring DSMB/C review

This clinical trial falls under the oversight of the DSMC.

The DSMC will initiate review following the enrollment of the first participant/or by the end of the year one if no accruals and will continue for the study lifecycle until there are no participants under active therapy and the protocol has closed to accrual. The DSMB will initiate review once the protocol is open to accrual.

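### The protocol text states no counted toxicity trigger for Part 2 of either arm; pausing an expansion is left to judgement

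*Combined protocol and SAP*

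**What the plan says.** **Part 1.** Sections 4.2 and 14.1 give counted rules: 2 or more DLTs in the first 3, or in 6, evaluable patients reject a dose. Section 15.3 limits the count: "The occurrence of any of the following AEs during Cycle 1" (Days 1 to 28).

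**Part 2.** Section 14.5 plans 2 × 28 = 56 efficacy-evaluable patients in Arm 1, with a goal of 60 enrolled, and as many as that in Arm 2. The one counted rule concerns response: "each expansion cohort will be deemed promising if at the end of the study at least 5 / 28 responses" are seen. The same section cites the institutional guideline on expansion cohorts to say that a sample size justification is not needed and that "requirements for stopping rules for lack of efficacy (futility) are also not required for cohorts of less than 30 patients". Toxicity is not mentioned there.

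**Whole trial.** Section 12.0: "The clinical trial may be discontinued or terminated in case of an unacceptable risk, any relevant toxicity". It also names events new in character, severity or frequency, without a number. Section 16.4: "The DSMC will initiate review following the enrollment of the first participant/or by the end of the year one" (if there are no accruals), continuing through the life of the study. On intensity it says "The degree of monitoring required will be determined based on level of risk and documented".

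**Other safeguards that run in Part 2.** Serious adverse event reporting (15.1, 15.2), dose interruption and discontinuation rules (15.4), eye examinations and echocardiograms at Cycle 3 and each odd cycle after it (Schedule of Assessments), and exclusion of patients with ocular risk factors (6.1, 6.2).

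**The concern.** The Part 2 safeguards either act on one patient or feed a review. None says how many events in an arm should pause accrual. Part 1 is a coarse filter of about 6 patients per dose, so a dose can pass by chance and then go to a whole expansion.

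Three features of this trial give that weight. Section 4.2 says that continuous dosing between the low intermittent dose and the older high doses has not been evaluated. Arm 2 may carry 8 mg BID continuous into expansion, while Section 3.2 reports DLTs on continuous dosing from 10 mg BID. And Section 3.2 places the retinal vein occlusions (RVO) after Cycle 1, where a Cycle 1 count cannot see them. As written, a reader cannot tell what event count the DSMC would act on.

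**Working it through.** **1. The plan's own figures reproduce.** With true DLT risk p, the standard 3+3 escalation probability is (1−p)³ + 3p(1−p)² × (1−p)³. At p = 0.1 to 0.5 this gives 0.906, 0.709, 0.494, 0.309, 0.172; the table in 14.1 shows 0.9, 0.7, 0.5, 0.3, 0.2. The 5/28 response rule gives exact type I error 0.142 at 10% and power 0.865 at 25%; 14.5 states 14% and 86%. No figure is given for a Part 2 toxicity rule.

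**2. How often a toxic dose passes 6 patients.** At Arm 1 Dose Level 1 and Arm 2 Dose Levels 2 and 3, the cohort is filled to 6 unless 2 of the first 3 have a DLT, and the dose passes with at most 1 of 6. Two DLTs in the first 3 already exceed 1 of 6, so P(pass) = (1−p)⁶ + 6p(1−p)⁵. The true rates are assumptions.

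| p | (1−p)⁶ | 6p(1−p)⁵ | P(pass) |
|---|---|---|---|
| 0.30 | 0.118 | 0.303 | 0.42 |
| 0.40 | 0.047 | 0.187 | 0.23 |
| 0.50 | 0.016 | 0.094 | 0.11 |

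**3. Exposure if no one intervened.** Taking 56 as an approximate denominator: 56 × 0.30 = 16.8, 56 × 0.40 = 22.4 and 56 × 0.50 = 28 patients with a Cycle 1 DLT. This is an upper bound, since it supposes that discretion is never used.

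**4. An example boundary.** Assumed: a 20% limit, a Beta(0.4, 1.6) prior (mean 0.20), a look every 7 patients, and a pause at the smallest count x with posterior P(rate > 0.20) > 0.95, where the posterior is Beta(0.4 + x, 1.6 + n − x). At n = 7, x = 3 gives 0.873 and x = 4 gives 0.970, so the boundary is 4. Over all looks: 4/7, 6/14, 8/21, 10/28, 12/35, 14/42, 15/49, 17/56.

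Exact operating characteristics, carrying the binomial count from look to look:

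| True rate | P(pause), 56 patients | P(pause), one cohort of 28 | Mean patients at pause | Mean DLT patients at pause |
|---|---|---|---|---|
| 3/19 | 0.04 | – | – | – |
| 1/6 | 0.05 | 0.04 | – | – |
| 0.20 | 0.13 | – | – | – |
| 0.30 | 0.65 | 0.42 | 26 | 10 |
| 0.40 | 0.97 | 0.80 | 19 | 8 |
| 0.50 | above 0.99 | 0.97 | 13 | 6 |

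The look at 56 can affect only about 60 − 56 = 4 enrolments. Without it the pause probabilities at 30%, 40% and 50% are 0.61, 0.95 and above 0.99.

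**5. Late RVO.** In 56 patients with RVO rate q, P(2 or more) = 1 − (1−q)⁵⁶ − 56q(1−q)⁵⁵. At assumed q of 1%, 2% and 5% this is 0.11, 0.31 and 0.78.

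**The case against.** **The trigger may exist elsewhere.** The institutional monitoring plan, the documented monitoring level and CR426 are cited but not supplied. This stands: what is shown is that this text prints no threshold, not that none exists.

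**Part 2 is not unmonitored.** A reader might infer that nothing protects expansion patients. The documents do not support that. The study is open-label, DSMC review runs throughout, and Section 12.0 allows termination for any relevant toxicity. The gap is a prespecified count at arm level, which is a design choice and contradicts nothing in the plan.

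**A 30% rate is borderline by the plan's own rule,** since Part 1 rejects at 2/6 (33%), and no document sets 20% or 30% as a limit. This stands; the limit is the sponsor's to choose.

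**Toxicity at 4 mg BID is probably acceptable.** The nearest figures, on an intermittent schedule, are rash as a DLT in 3/19 (15.6) and one Grade 3 related event in 20 adults (3.2). This stands for 4 mg BID but does not cover 8 mg BID continuous.

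**The denominators differ.** The 56 are efficacy-evaluable patients, whereas the boundary counts DLT-evaluable ones. Section 14.1 also brings Part 1 patients treated at the recommended dose into the efficacy analysis. So 56 is only an approximation.

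**A stronger reading to avoid.** A reader might infer that in Arm 2 the 4 mg dose can become the recommended dose on 3 patients. Section 4.2 escalates "If 0 of the first 3 evaluable subjects in Dose Level 1 exhibit a DLT in Cycle 1", and if at least "2 of the 6 evaluable subjects in Dose Level 2 exhibit a DLT in Cycle 1, then mirdametinib 4 mg BID PO" becomes the recommended dose. But 14.1 also says that at most 1 of the first 3 leads to expansion of Dose Level 1, which would include 0 of 3. The two texts conflict, so no probability should be attached to that path.

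**Conclusion.** The point holds as a statement about this protocol's text: neither arm has a counted toxicity trigger in Part 2, and the futility waiver does not speak to toxicity. A dose with an assumed 30% to 50% Cycle 1 DLT rate passes 6 patients with probability 0.42 to 0.11, after which pausing rests on case-by-case judgement. It is a worthwhile, inexpensive improvement rather than an error. Confidence is medium, because the institutional sources were not available and because the true rates, prior, limit and cut are assumptions.

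**What to change.** **First**, if the institutional monitoring plan, the documented monitoring level or CR426 already sets a trigger, state it in 16.4.

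**Otherwise**, add to 4.2 (Part 2) and 16.4, and refer to it in 12.0:

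- Pool the cohorts within an arm, which share one recommended dose. Count DLT-evaluable Part 2 patients with a Section 15.3 event in Cycle 1. The sponsor decides whether to include Part 1 patients treated at that dose and recomputes the boundary if so.
- Pause new enrolment for DSMC review at a stated boundary, such as the 20% example above. A 30% limit (posterior P(rate > 0.30) > 0.90, Beta(0.6, 1.4) prior) gives 4/7, 7/14, 10/21, 12/28, 15/35, 17/42, 20/49, 22/56. It pauses with probability 0.02 at 1/6, but only 0.26 at 30% and 0.74 at 40%.
- Require expedited DSMC review of RVO in any cycle, no later than the second case in an arm. Section 3.2 gives the precedent: the lung cancer trial of this drug suspended enrolment after a second RVO in the Phase 1 trial.
- At each look, also give the DSMC the number of patients who stopped drug for related toxicity in any cycle.
- State the operating characteristics in 14.5.

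**Cost.** Wording and tallies of data already collected, for a committee already in place; dosing is unchanged. At about 2 patients per month and a 28-day cycle, about 2 patients are still in Cycle 1 at a look, so enrolment need not be held between looks. The named downside is false pauses: 0.04 to 0.05 at rates of 3/19 to 1/6 and 0.13 at 20% under the 20% boundary. An RVO review would be called in 11% of arms of 56 even if the true rate were 1%.

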13.0 CRITERIA FOR OUTCOME ASSESSMENT AND ENDPOINT EVALUABILITY

13.1 Safety Endpoints

Tolerability and safety of mirdametinib and mirdametinib plus fulvestrant combination, endpoints of the study, will be evaluated by assessment of AEs, TEAEs, SAEs, DLTs, concomitant medications, PEs, vital sign measurements, clinical safety laboratory evaluations (hematology, serum chemistry, and urinalysis), ECOG scores, electrocardiograms (ECGs), and other assessments.

All safety parameters will be performed in accordance with the Schedules of Assessments presented in each arm.

Memorial Sloan Kettering Cancer Center
[name]
[name]

